4.4. Safety Analysis Set

The Safety Analysis Set (SAF) comprises all subjects who were randomized and received at least one treatment (i.e., any dose of Princess® FILLER Lidocaine or the control medical device). The analyses based on the SAF will use the actual treatment groups.

The SAF will be used for all analyses of safety endpoints.

4.5. Protocol Deviation and Non-Compliances

Non-compliances are unplanned deviations from applicable regulations, guidelines, other standards, controlled documents, contractual agreements, and/or protocol or project specific requirements. Any change, divergence, or departure from the study design or procedures defined in the protocol; a subset of non-compliances occurring at an individual subject level, or deviations that are related to COVID-19 are defined as protocol deviations (PDs).

All subjects who comply with criteria for inclusion into FAS, PPS and SAF, as defined in section 4, will be included in respective analyses.

Protocol deviations will be identified (in a blind manner) and discussed throughout the study. Prior to database lock, all protocol deviations will be listed in a blinded manner. Their relevance (minor / major) and their impact on the effectiveness assessments, i.e., with respect to exclusion of subjects from PPS and/or FAS will be evaluated in the Blind Data Review Meeting (BDRM). Possible major protocol deviations may include but are not limited to deviations related to premature termination, the inclusion and exclusion criteria, and prohibited concomitant treatments.

For the preparation of the BDRM, subject listings will be generated with all protocol deviations and non-compliances identified from eCRF entries and from monitoring documentation system. These listings

This document is confidential.

will be reviewed by Croma Pharma and SH study team. The final decision with regards to protocol deviations and populations will be taken in the BDRM.

The number and percentage of subjects with a protocol deviation by type of deviation category will be presented by treatment group. In addition, protocol deviations related to COVID-19 will be summarized in a similar fashion.

All protocol deviations will be provided in a by-subject listing with the categorization of minor or major. Protocol deviations related to COVID-19 will be listed separately.

Primary reasons and categories of the PDs at individual subject levels are:

- Concomitant Medication
- Dosing
- Enrollment Criteria
- Informed Consent
- Laboratory
- Non-compliance
- Other
- Regulatory
- Visit Schedule
- Visit/Procedure Required

This document is confidential.

5. Estimands

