4.2. Full Analysis Set

The Full Analysis Set (FAS) consists of all randomized subjects who received Princess® FILLER Lidocaine AND the control Juvéderm® Ultra XC at the same visit as initial treatment; subjects who receive only one treatment (only Princess® FILLER Lidocaine or only Juvéderm® Ultra XC) during initial treatment will be excluded from the FAS. The analyses based on the FAS will use the randomized treatment groups.

The FAS will be used for effectiveness, demographic, and other baseline characteristics analyses.

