5.1. Primary Effectiveness Endpoint

The estimand for the primary effectiveness endpoint is defined as follows:

- Treatment: Princess® FILLER Lidocaine and Juvéderm® Ultra XC for the treatment of NLF (both sides) in each subject.
- Population: Of all subjects defined by the study inclusion / exclusion criteria, the analysis population will include subjects who were randomized to the study treatment and received both treatments (Princess® FILLER Lidocaine and the control medical device) as initial treatment at the same visit (FAS population).
- Variable: A binary variable indicating the subject is alive and has a NLF-SRS response based on the independent blinded evaluating investigator live assessment using the NLF-SRS at Week 24 after initial treatment and relative to baseline assessments. NLF-SRS responder with regards to each specific NLF is defined as a subject with at least one grade improvement from baseline in NLF-SRS in that NLF.
- Intercurrent events:
 - The intercurrent event 'death' is very unlikely in this study, however, in case of death prior to Week 24, this will be considered as non-response following the composite strategy.
 - Major protocol deviations impacting the NLF-SRS assessment will be handled using the treatment-policy strategy, i.e., the NLF-SRS value at Week 24 will be used for categorization of response.
- Population-level summary: Paired difference of NLF-SRS response rates between Princess® FILLER Lidocaine and the control medical device for non-inferiority comparison.

Study discontinuation (due to any reason) prior to Week 24 is not considered as an intercurrent event, however this will lead to missing Week 24 values, which will be imputed using single imputation strategy as non-response for the primary analysis of this estimand. Subjects with missing NLF-SRS value at Baseline will be considered as non-response for the primary analysis of this estimand.

5.2. Key Secondary Effectiveness Endpoint 1

The estimand for the key secondary effectiveness endpoint 1 is defined as follows:

- Treatment: Princess® FILLER Lidocaine and Juvéderm® Ultra XC for the treatment of NLF (both sides) in each subject.
- Population: Of all subjects defined by the study inclusion / exclusion criteria, the analysis population will include subjects who were randomized to the study treatment and received both treatments (Princess® FILLER Lidocaine and the control medical device) as initial treatment at the same visit (FAS population).

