The FAS and the PPS will be both considered equally important for the primary analysis. The primary effectiveness analysis will be performed with the FAS; if Princess® FILLER Lidocaine can be considered non-inferior to Juvéderm® Ultra XC according to this analysis, the results of the non-inferiority comparison based on the PPS can be considered confirmatory. Otherwise, the results of this analysis has to be considered exploratory. Overall non-inferiority is demonstrated only if the results are consistent for both analysis data sets. All secondary and additional effectiveness analyses will be conducted for the FAS and PPS.

A hierarchical testing procedure will be applied for the analysis of the primary outcome measure, as well as the key secondary outcome measures, in order to control multiplicity. At this, the following order will be used:

1. Analysis of primary effectiveness based on FAS
2. Analysis of primary effectiveness based on PPS
3. Analysis of key secondary effectiveness # 1 based on FAS
4. Analysis of key secondary effectiveness # 1 based on PPS
5. Analysis of key secondary effectiveness # 2 based on FAS
6. Analysis of key secondary effectiveness # 2 based on PPS

All statistical presentation will be done by treatment group (Princess® FILLER Lidocaine and Juvéderm® Ultra XC). For the primary analysis of the estimands of the primary effectiveness and of key secondary effectiveness endpoints, missing Week 24 assessments of NFL-SRS will be imputed by single imputation as no response. As sensitivity analyses, a best-case analysis (missing values for Princess® FILLER Lidocaine will be considered as a response, missing values for Juvéderm® Ultra XC will be considered as a non-response), a worst-case analysis (missing values for Princess® FILLER Lidocaine will be considered as a non-response, missing values for Juvéderm® Ultra XC will be considered as a response) will be performed on the FAS. Additionally, a tipping point analysis will be conducted on FAS to investigate the robustness of the results, and a complete-case analysis (includes subjects without any missing data) will be performed as supportive analysis.

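### SAP 4.5 lets the blind data review consider removing protocol deviators from the FAS, which conflicts with the FAS definition in 4.2 and the primary estimand in 5.1

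*SAP*

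**What the plan says.** **FAS definition.** SAP 4.2: "The Full Analysis Set (FAS) consists of all randomized subjects who received Princess® FILLER Lidocaine AND the control" device at the same visit as initial treatment. It gives one exclusion: "subjects who receive only one treatment (only Princess® FILLER Lidocaine or only Juvéderm® Ultra XC) during initial treatment will be excluded from the FAS". Protocol 14.1 has the same rule. Both documents use major deviations to define the PPS, not the FAS (SAP 4.3, protocol 14.1).

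**Estimand.** SAP 5.1 takes the FAS as the population and states: "Major protocol deviations impacting the NLF-SRS assessment will be handled using the treatment-policy strategy", so the observed Week 24 grade is used. Discontinuation before Week 24 leads to a missing value, which is imputed as non-response. Sections 5.2 and 5.3 do the same for the two key secondary endpoints.

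**Deviation review.** SAP 4.5 has the relevance of deviations and their impact on the effectiveness assessments judged "with respect to exclusion of subjects from PPS and/or FAS will be evaluated in the Blind Data Review Meeting (BDRM"). It adds: "The final decision with regards to protocol deviations and populations will be taken in the BDRM". On what counts as major: "Possible major protocol deviations may include but are not limited to deviations related to premature termination", followed by eligibility criteria and prohibited concomitant treatments. The same section also says: "All subjects who comply with criteria for inclusion into FAS, PPS and SAF, as defined in section 4, will be included in respective analyses".

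**Use of the two sets.** SAP section 8 opens: "The FAS and the PPS will be both considered equally important for the primary analysis". It then requires consistent results in both sets before non-inferiority is claimed, and tests FAS and PPS as separate steps for the primary and both key secondary endpoints.

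**The concern.** Under 4.2 and 5.1, a subject who received both fillers and later deviated belongs in the FAS. Under 4.5, the meeting may consider removing that subject from the FAS because of the deviation. Both rules cannot govern the same subject.

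Three things are at stake.

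1. **The estimand.** Treatment policy for major deviations has no meaning if the deviators can be removed first.
2. **The missing-data plan.** Premature termination is the first example of a possible major deviation in 4.5. If these subjects leave the FAS, they drop out of the non-response imputation and of the best-case, worst-case and tipping-point analyses. SAP 8.4 plans the tipping-point analysis on the FAS only.
3. **The two-set safeguard.** The PPS is the FAS without major deviators up to Week 24. The more of those subjects also leave the FAS, the less the FAS result adds to the PPS result.

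**Working it through.** **1. The rules side by side**

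| Subject (both devices given at initial visit) | SAP 4.2 / protocol 14.1 | SAP 5.1 | SAP 4.5 |
|---|---|---|---|
| Major deviation, Week 24 grade present | in FAS | grade used | exclusion from FAS may be evaluated |
| Discontinued before Week 24 | in FAS | non-response | same, if judged a major deviation |
| Given only one device | out of FAS | outside the population | consistent with 4.2 |

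Only the last row agrees across all the texts. SAP section 11 lists no change to the FAS rule, and protocol 17.2 provides for a blind review of deviations without giving it authority over the FAS.

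**2. The plan's own figure**

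Inputs from SAP 2.7: response 87% (test) and 88% (control), independent folds, margin -10%, one-sided 95% limit, N = 222 for 90% power. Discordant proportion: 0.87 × 0.12 + 0.13 × 0.88 = 0.2188.

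- Closed form: N = (1.645 + 1.282)² × (0.2188 - 0.01²) / 0.09² ≈ 231.
- Simulated power at N = 222 with the Newcombe-Wilson limit: 88.4%.
- The plan used 1600 simulations, with standard error √(0.9 × 0.1 / 1600) = 0.75 points, so 90% at 222 is reproduced to within about 2 points.

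Nothing in this point changes that figure. The steps below use one-sided 0.025, as in the test in SAP 8.2.1. The difference between that level and the one in 2.7 is a separate matter.

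**3. How many subjects the clause could touch**

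SAP 2.6 plans 270 randomised and at least 240 evaluable after drop-outs and major deviations: 270 - 240 = 30, or 11%.

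**4. Effect on the chance of success**

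Wald limit; 240 compliant subjects at 87% and 88%. The deviators' rates are assumptions.

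| Analysis set | Chance of success |
|---|---|
| 30 removed (240 analysed) | 84.5% |
| 30 kept, responding like the rest | 88.5% |
| 30 kept, all non-response on both sides | 92.4% |
| 30 kept, 70% test vs 88% control | 68.3% |
| 30 kept, 50% test vs 88% control | 36.7% |

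Removing subjects scored as non-response on both sides lowers the chance of success (92.4% to 84.5%). Removing subjects who failed mainly on the test side raises it (68.3% or 36.7% to 84.5%).

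**5. Effect on false non-inferiority**

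Assumed: n = 270, control 88%, test 78% (true difference exactly -10%). Test-only and control-only response are 0.0936 and 0.1936 with independent folds, or 0.03 and 0.13 with correlated folds.

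| Removal | Independent | Correlated |
|---|---|---|
| 3, 5 or 27 subjects, unrelated to outcome | 2.6-2.7% | 3.1-3.2% |
| 5 both-side failures | 2.3% | 2.6% |
| 10 both-side failures | 2.2% | 2.2% |

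The first row matches the rate with nobody removed, so such removal causes no inflation.

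**6. A constructed example in which the verdict changes**

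Cells are both / test only / control only / neither; lower limit = D - 1.96 × √[(discordant share - D²)/n].

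- 240 compliant subjects, 183/24/29/4: D = -5/240 = -2.1%; SE = √[(53/240 - 0.0208²)/240] = 3.03%; lower limit -8.0%. Pass.
- Add 30 deviators, 15/2/11/2, giving 198/26/40/6: D = -14/270 = -5.2%; SE = √[(66/270 - 0.0519²)/270] = 2.99%; lower limit -11.1%. Fail.

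With the FAS as defined in 4.2, non-inferiority is not shown. With the deviators out of both sets, it is. The counts are invented to show that the clause can matter; they are not a forecast.

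**The case against.** Section 4.5 itself says that subjects who meet the section 4 criteria will be included. Read that way, the meeting only applies 4.2. There is also a harmless meaning for the reference to the FAS: being given only one device is itself a deviation, dosing is a listed deviation category, and 4.2 does exclude that case. This reading is possible and may be what was intended. But the text does not limit the clause to it, its examples are of a different kind, and the final decision on populations stays with the meeting. Section 4.5 is therefore inconsistent within itself rather than a clean override of 4.2.

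The estimand population in 5.1 is also framed by the inclusion and exclusion criteria, so removing an ineligible subject is less plainly contrary to 5.1 than removing other deviators. That stands, although 4.2 contains no such exclusion.

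Finally, the review is blinded, and this does limit selective removal. A reader might infer that the meeting could see Week 24 grades by side and drop unfavourable faces. The documents do not say so: 4.5 describes listings of deviations and non-compliances, and SAP 2.8 withholds the allocation until the database is cleaned and closed. Dropping 3 or 5 faces in which only the test fold failed would raise false non-inferiority to about 5.5% or 8.6% (independent folds), but that requires knowledge of both filler and outcome, so these figures do not describe this plan. Blinding does not, however, restore an estimand from which deviators have been removed.

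**Conclusion.** The conflict is on the face of the SAP and concerns the primary analysis set of a pivotal non-inferiority trial. It should be corrected. Used on anyone other than a subject given only one device, the clause departs from 4.2. For major deviators with a Week 24 grade and for drop-outs, it also undoes the handling stated in 5.1.

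The size depends on how many of the roughly 30 subjects were removed and how they responded, and the sign can go either way. No systematic inflation of error follows from removal unrelated to outcome. The constructed change of verdict rests on deviators who failed mainly on the test side.

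A reader might infer that the two required analyses become one. That happens only if every subject excluded from the PPS is also removed from the FAS, which the plan does not prescribe. Partial removal brings the sets closer and weakens the comparison by degree.

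**What to change.** In SAP 4.5, delete *and/or FAS*, or limit it to the 4.2 criterion. Add that:

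- FAS membership is set only by 4.2 (randomised, and both devices given at the same initial visit);
- no other deviation removes a subject from the FAS;
- the blind data review meeting decides only minor/major status and PPS membership.

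The word *other* is needed because being given only one device is a deviation that 4.2 does exclude. The sentence giving the meeting the final decision on populations should be narrowed to match.

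The cost is a few words in the SAP. No sample size, test or data collection changes.

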5.1. Primary Effectiveness Endpoint

The estimand for the primary effectiveness endpoint is defined as follows:

- Treatment: Princess® FILLER Lidocaine and Juvéderm® Ultra XC for the treatment of NLF (both sides) in each subject.
- Population: Of all subjects defined by the study inclusion / exclusion criteria, the analysis population will include subjects who were randomized to the study treatment and received both treatments (Princess® FILLER Lidocaine and the control medical device) as initial treatment at the same visit (FAS population).
- Variable: A binary variable indicating the subject is alive and has a NLF-SRS response based on the independent blinded evaluating investigator live assessment using the NLF-SRS at Week 24 after initial treatment and relative to baseline assessments. NLF-SRS responder with regards to each specific NLF is defined as a subject with at least one grade improvement from baseline in NLF-SRS in that NLF.
- Intercurrent events:
 - The intercurrent event 'death' is very unlikely in this study, however, in case of death prior to Week 24, this will be considered as non-response following the composite strategy.
 - Major protocol deviations impacting the NLF-SRS assessment will be handled using the treatment-policy strategy, i.e., the NLF-SRS value at Week 24 will be used for categorization of response.
- Population-level summary: Paired difference of NLF-SRS response rates between Princess® FILLER Lidocaine and the control medical device for non-inferiority comparison.

Study discontinuation (due to any reason) prior to Week 24 is not considered as an intercurrent event, however this will lead to missing Week 24 values, which will be imputed using single imputation strategy as non-response for the primary analysis of this estimand. Subjects with missing NLF-SRS value at Baseline will be considered as non-response for the primary analysis of this estimand.

5.2. Key Secondary Effectiveness Endpoint 1

The estimand for the key secondary effectiveness endpoint 1 is defined as follows:

- Treatment: Princess® FILLER Lidocaine and Juvéderm® Ultra XC for the treatment of NLF (both sides) in each subject.
- Population: Of all subjects defined by the study inclusion / exclusion criteria, the analysis population will include subjects who were randomized to the study treatment and received both treatments (Princess® FILLER Lidocaine and the control medical device) as initial treatment at the same visit (FAS population).
- Variable: A binary variable indicating the subject is alive and has NLF-SRS response based on the independent blinded photographic reviewers (I, II, and III) assessments of photograph (NLF severity) using the NLF-SRS at Week 24 after initial treatment compared to baseline. NLF-SRS responder with regards to each specific NLF is defined as a subject with at least one grade improvement from baseline in NLF-SRS in that NLF.
- Intercurrent events:
 - The intercurrent event 'death' is very unlikely in this study, however, in case of death prior to Week 24, this will be considered as non-response following the composite strategy.

This document is confidential.

- Major protocol deviations impacting the NLF-SRS assessment will be handled using the treatment-policy strategy, i.e., the NLF-SRS value at Week 24 will be used for categorization of response.
- Population-level summary: Paired difference of NLF-SRS response rates between Princess® FILLER Lidocaine and the control medical device for non-inferiority comparison.

Missing data imputation for this estimand will be performed as described for the primary estimand.

5.3. Key Secondary Effectiveness Endpoint 2

The estimand for the key secondary effectiveness endpoint 2 is defined as follows:

- Treatment: Princess® FILLER Lidocaine and Juvéderm® Ultra XC for the treatment of NLF (both sides) in each subject.
- Population: Of all subjects defined by the study inclusion / exclusion criteria, the analysis population will include subjects who were randomized to the study treatment and received both treatments (Princess® FILLER Lidocaine and the control medical device) as initial treatment at the same visit (FAS population).
- Variable: A binary variable indicating subject is alive and has NLF-SRS response based on the treating investigator live assessment using the NLF-SRS at Week 24 after initial treatment compared to baseline. NLF-SRS responder with regards to each specific NLF is defined as a subject with at least one grade improvement from baseline in NLF-SRS in that NLF.
- Intercurrent events:
 - The intercurrent event 'death' is very unlikely in this study, however, in case of death prior to Week 24, this will be considered as non-response following the composite strategy.
 - Major protocol deviations impacting the NLF-SRS assessment will be handled using the treatment-policy strategy, i.e., the NLF-SRS value at Week 24 will be used for categorization of response.
- Population-level summary: Paired difference of NLF-SRS response rates between Princess® FILLER Lidocaine and the control medical device for non-inferiority comparison.

Missing data imputation for this estimand will be performed as described for the primary estimand.

This document is confidential.

6. General Aspects for Statistical Analysis

6.1. General Methods

- All analyses and summaries will be produced using Statistical Analysis System (SAS®) version 9.4.
- Unless otherwise specified, summaries for disposition and demography will be presented by treatment group and overall, all other summaries will be presented by treatment/treatment group.
- Continuous variables will be summarized using the number of observations (n), mean, standard deviation (SD), median, minimum, and maximum. Categorical variables will be summarized using number of observations (n), frequency and percentages of subjects. Summary statistics will be presented to the following degree of precision (see [Table 2](#)):

Table 2 Reporting Precision

Statistics	Degree of Precision
Mean, Median, Confidence limit boundaries	One more decimal place than the raw data e.g. if data is displayed to 3 decimal places: data=0.xxx, output=0.xxxx
Standard deviation (SD)	Two more decimal places than the raw data e.g. if data is displayed to 3 decimal places: data=0.xxx, output=0.xxxxx
Minimum, Maximum	The same number of decimal places as the raw data
P-value	Rounded to 3 decimal places and formatted as 0.xxx; P-values smaller than 0.001 as '<0.001'; P-values smaller than 0.0001 as '<0.0001'
Percent	One decimal place

- All relevant subject data will be included in listings. All subjects entered into the database will be included in subject data listings.

6.2. Key Definitions

The study day is the day relative to the date of first administration of Investigational Medical Device (IMD), where Day 1 is the day of first administration of IMD.

The first dose date is defined as the first non-missing date where an administration of IMD was recorded. The last dose date is defined as the last non-missing date where an administration of IMD was recorded.

For on-treatment events (on or after first dosing day), Study Day = Event Date - date of first administration of IMD + 1; and for pre-treatment events (prior to first dosing day), Study Day = Event Date - administration of IMD.

Unless otherwise specified, baseline is the last non-missing observation before the administration of IMD, which is expected to be Day 1, or Screening if the Day 1 data are not available.

This document is confidential.

